## Chapter 1 : INTRODUCTION

Pneumonia thought to be the chief aetiological process in the development of pleural space infection is defined as an infection of the lung parenchyma with an estimated annual incidence rate of 5–11 cases per 1000 population, with around 50,000 hospital admissions in the UK per year (1). Parapneumonic effusions caused by an infection of the pleural membranes occur in 40–57% of cases of pneumonia. A variable percentage (10–20%) of parapneumonic effusions progresses to empyema (pus) and/or abscess formation (encapsulation). Pleural infection is associated with significant morbidity and mortality which may be as high as 20–35% in immunocompromised patients (1)

Standard treatment of these collections in adults involves antibiotic therapy, effective drainage of infected fluid and surgical intervention if conservative management fails. For parapneumonic effusions which require clearance, appropriate therapy is effective drainage via an intercostal catheter (ICC) with antibiotic therapy. Frequently, simple ICC drainage is not effective due to the presence of loculations, formed predominantly by fibrinous material deposited in the fibrinopurulent phase of empyema, which prevent free drainage of infected pleural fluid (2). The presence of fibrinous septae in the pleural space, known as loculations, may result in inadequate drainage of effusions and therefore non-resolution of infection and systemic sepsis. Without effective intercostal catheter drainage, surgical intervention (VATS or open) has usually been required to clear loculations for resolution of infection.

Non-surgical treatment options to reduce the impact of adhesions and locule include (in addition to appropriate antibiotic therapy) single and multiple thoracocentesis, or single and multiple intercostal tube thoracostomies, with or without intrapleural fibrinolytic agents. Surgical options include direct-vision and VATS adhesiolysis, limited and full thoracotomy with adhesiolysis, and decortication for severe pleural thickening (3).

Although the success rate of surgical intervention remains high, the morbidity and mortality of both VATS and open thoracotomy are of concern, particularly in a cohort of patients who may be

older and with significant co-morbidity. Less invasive therapies which promote pleural space drainage and effective resolution of pleural infection are therefore likely to be of considerable clinical utility (4).

Intra-pleural fibrinolytic therapy (IPFT) in the management of complex parapneumonic effusions and thoracic empyema has been employed for over 50 years, with a mixture of agents including streptokinase/streptodornase (5), streptokinase (6,7,8,9), urokinase (10), alteplase (11,12), and a combination of streptodornase and alteplase (13). These medications are administered into the pleural space via an ICC.

Fibrinolytic agents including streptokinase, urokinase, alteplase and recombinant tissue plasminogen activator (rTPA) have been used safely and effectively intrapleurally for complicated pleural effusion and empyema (14,15,16,17). During the fibrinopurulent-purulent stage of empyema, there is an imbalance between fibrin activators and fibrin inhibitors (18), with elevated levels of plasminogen activator inhibitor (PAI-1) resulting from the presence of inflammation-induced tumour necrosis factor-alpha, interleukin 8 and transforming growth factor beta, as well as lower levels of endogenous tissue plasminogen activator (tPA) (19). This results in a pro-fibrotic state causing deposition of fibrin-forming loculations within the infected pleural space (20). Fibrinolytic agents activate plasmin, lysing fibrinous septations, thereby improving pleural fluid drainage and clearing infection without requiring surgical intervention.

MIST 2 trial has established intrapleural therapy as the mainstay of CPEE treatment hence avoiding surgery and decreasing the length of hospitalization [10,21, 22, 23, 24]; however, little is known about the correct dosage needed for tPA and DNase [25]. Dose and duration of intrapleural therapy based on MIST 2 involve multiple dosing and can be time-consuming for health care providers [21, 25]. Previous studies showed that complexity of treatment is a factor associated with poor adherence to a regimen [26]. For this reason, trying to find the minimum effective dose and simplifying the regimen is essential for minimizing side effects and maximizing adherence. The review of currently available literature shows concurrent administration of tPA and DNase to be safe and effective even at lower cumulative dose

Other study was carried out in May 2022 in which Modified regimen intrapleural alteplase 16 mg t-PA with 5 mg DNase for total 3 doses that administered sequentially within 24 h had been used. In this study, modified regimen of t-PA and DNase offer an alternative therapeutic option for patients that are unfit or refuse surgical intervention but persistent pleural infection. They have demonstrated similar treatment success comparable to other studies [24, 27, 28], as evidenced by improvement on pleural fluid drainage and reduction in pleural opacity on day 7 chest x-ray was approximately 50% from the baseline using intrapleural 16 mg t-PA with 5 mg DNase. The mechanism of action of t-PA and DNase in pleural cavity remain unclear. Studies suggested that IPFT may trigger the monocyte chemoattractant protein 1 (MCP-1) pathway which promote pleural fluid formation and subsequently causes a therapeutic lavage effect that increases pleural fluid drainage [29]

Another option for intrapleural therapy may be pleural irrigation with normal saline. The idea behind is to dilute and remove bacteria, cytokines, inflammatory cells, and pro-fibrinogenic coagulation factors, which induce pleural fluid organization. Also, the mechanical process of irrigation increases pleural fluid drainage by reducing stasis and organization of the intrapleural contents .

A randomised controlled pilot study in which saline pleural irrigation (three times per day for 3 days) plus best-practice management was compared with best-practice management alone was performed in patients with pleural infection requiring chest-tube drainage. The primary outcome was percentage change in computed tomography pleural fluid volume from day 0 to day 3. Patients receiving saline irrigation had a significantly greater reduction in pleural collection volume on

computed tomography compared to those receiving standard care. Significantly fewer patients in the irrigation group were referred for surgery (30).

However, till date there is no study done on head to head comparison between intrapleural fibrinolytic with alteplase and DNase Versus Pleural irrigation with normal saline.

The respiratory unit in HUKM has been using intrapleural fibrinolysis therapy with varying doses since 2017. This study aims to develop an algorithm for intrapleural therapy on pleural infection with a minimally invasive method without surgical intervention. It also aims to determine the efficacy and safety of this dose regimen of combined intrapleural Alteplase and DNase versus pleural irrigation on management of pleural infection.

## CHAPTER 2 : RESEARCH OBJECTIVES & HYPOTHESIS

### 2.1 Research Questions:

- Is the combination of intrapleural Alteplase (t-PA) 5mg and DNase (Pulmozyme) 5mg superior than pleural irrigation in the management of pleural infection?

### 2.2 Primary Objective:

- To measure the volume of pleural effusion drainage (in mls) 48 hours following randomization

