### 2.3 Secondary Objectives:

- To determine the reduction of pleural opacity (in percentage) on chest radiograph from day 1 (randomization) to day 7
- To determine the change on inflammatory markers (WBC/CRP) from day 1 (randomization) to day 7
- To determine the outcome :
  - Length of hospital stay (in days) after randomization for each group
  - The need of surgical intervention in 30 days
  - Adverse effects following t-PA/DNase and pleural irrigation
  - Mortality rate at 30 days

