### Medication Regimen :

t-PA (Alteplase) 5mg and DNase (Pulmozyme)5mg

t-PA (Alteplase) that is available in our pharmacy is 50mg ampoule and DNase (Pulmozyme) is 2.5mg per ampoule

The number of installation of intrapleural t-PA/DNase depends on the discretion of the treating physician (at least 6 hours apart between each dose). 5mg of Alteplase (t-PA) and 5mg DNase are diluted in each 50ml of 0.9% sodium chloride solution. t-PA and DNase are not mixed together in one syringe. The detailed method of t-PA/DNase therapy administration is described in Appendix 1. In brief, both medication are administered sequentially which t-PA is first instilled intrapleurally and the chest tube is then clamped for 45 minutes, then unclamped to allow free drainage for 45 minutes. The same procedure is then repeated for DNase. Selection of the timing of treatment and removal of chest tube are depending on the chest physician's judgement.

However, as for patients who were randomized into pleural irrigation group, subjects were administered 250 ml of 0.9% sodium chloride via chest tube a three way tap from a drip stand which were allowed drainage freely over 1 hour. Pleural irrigation will be performed minimum of 3 installations and maximum of 9 installation (3 times per day).

Both groups received standard care of treatment : which includes regular flushing of chest drain to maintain patency using 20mls of normal saline.

The primary outcome was to evaluate the volume of pleural effusion drainage (in mls) 72 hours following randomization. The volume drained measured after subtracting the amount of volume administered as per protocol.

The secondary outcome are measured by the change in the area of pleural opacity in chest x-ray (day 7 post t-PA/DNase compared to baseline), measured as the percentage of the ipsilateral hemithorax occupied by effusion. The area of pleural opacity and the area of the ipsilateral hemithorax will be measured digitally by two radiologists using Horos Project Software, v3.2.1 as described previously in Multicentre Intrapleural Sepsis Trial 2 (MIST-2)

Other outcomes that will be monitored include :

1. Inflammatory markers including serum C-reactive protein (CRP) & white blood count
2. Length of hospital stay in days
3. The need of surgical intervention within 30 days
4. Adverse effects :
  - a. Chest pain required escalation of analgesics
  - b. Systemic bleeding
  - c. Pleural bleeding

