During any point of treatment subjects will be allowed to cross-over and analysis will be done as per intention to treat. Subjects in the pleural irrigation group may be switched to IPFT group if there is poor response to treatment (poor drainage of effusion), or adverse effects of irrigation as per clinician's judgement. On the contrary, subjects in the IPFT group may be switched to pleural irrigation group if patient developed any adverse effects of IPFT (e.g hemothorax, haemoptysis). Those who failed both treatment will be referred for surgical intervention

Monitoring Parameters :

a. Pleural irrigation group

Parameter	Day0	Day1	Day2	Day3	Day7	Day30
Investigations						

 
• Full blood count (FBC)               
 
○ WBC
 
○ Hemoglobin
 
 
 
	√	√	√	√	√	
• C- reactive protein (CRP)	√				√	
• Chest X-ray	√				√	
• Ultrasound Thorax	√	√	√	√		
Adverse effects						
• Chest pain required escalation of analgesics		√	√	√		
• Gastrointestinal bleed		√	√	√		
• Bleeding from chest drain site		√	√	√		
• Intrapleural hemorrhage		√	√	√		
• Hemoptysis		√	√	√		
• Clinical deterioration – hypotension, dyspnea		√	√	√		
• Hb drop >10% required transfusion blood		√	√	√		
• Death related to intrapleural saline irrigation		√	√	√		

Others Outcome						
• Mortality						
• Surgical intervention						

b. IPFT group

Net Volume of pleural fluid drained (ml) post pleural irrigation	Baseline	Day 1	Day 2	Day 3
	√	√	√	√
Cumulative pleural fluid drained post pleural irrigation				√

b. Intrapleural fibrinolytic group

Parameter	Day0	Day1	Day2	Day3	Day7	Day30
Investigations						
• Full blood count (FBC) 
 
○ WBC
 
○ Hemoglobin
 
	√	√	√	√	√	
• C- reactive protein (CRP)	√				√	

• Chest X-ray	√				√	
• Ultrasound Thorax	√	√	√	√		
Adverse effects						
• Chest pain required escalation of analgesics		√	√	√		
• Gastrointestinal bleed		√	√	√		
• Bleeding from chest drain site		√	√	√		
• Intrapleural hemorrhage		√	√	√		
• Hemoptysis		√	√	√		
• Clinical deterioration – hypotension, dyspnea		√	√	√		
• Hb drop >10% required transfusion blood		√	√	√		
• Death related to intrapleural therapy		√	√	√		
Others Outcome						
• Mortality						
• Surgical intervention						

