Net Volume of pleural fluid drained (ml) post IPFT	Baseline	Day 1	Day 2	Day 3
	√	√	√	√
Cumulative pleural fluid drained post IPFT				√

[figure not shown]
Operational Definition:

[figure not shown]
- Treatment success: significant amount of pleural drainage post intervention, reduction of opacity on chest x-ray and resolution of inflammatory markers on day 7 without surgical intervention within 30days
- Treatment failure:
  - Poor drainage from chest drain, failure of resolution of pleural effusion or empyema at least 50% reduction on opacity on chest x-ray and clinical evidence of ongoing infection that requires surgical intervention within 30days post randomization or death before discharge.

All patients will be followed up in respiratory clinic day 30 after discharge or phone call if patient defaulted clinic appointment.

Data will be collected prospectively (Appendix 5) by reviewed patient demographics, clinical data on length of hospital stay, pleural fluid analysis, intrapleural therapy, radiographic characteristics, adverse events, Laboratory data (blood leukocyte count, C-reactive protein, haemoglobin level), Intrapleural therapy data including number of chest tubes, duration of chest tube in pleural cavity and cumulative volume of pleural fluid drained. Besides that, length of hospital stay, treatment outcomes, surgical interventions and the occurrence of complications are recorded.

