### Data Collection Sheet

**Open label controlled trial of pleural irrigation with normal saline versus intrapleural fibrinolytic with tissue plasminogen activator and DNase in Pleural Infection in Universiti Kebangsaan Malaysia Medical Centre (UKMMC)**

Patient's ID sticker

Date of admission:

Admission ward:

Date of discharge :

Phone number:

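### The primary drainage volume is set at 48 hours in one section and 72 hours in another, and the Day 3 cumulative field does not settle which applies

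*Combined protocol and SAP*

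**What the plan says.** Section 2.2 gives the primary objective: "To measure the volume of pleural effusion drainage (in mls) 48 hours following randomization". Section 3.6, under Medication Regimen, says: "The primary outcome was to evaluate the volume of pleural effusion drainage (in mls) 72 hours following randomization". It adds that the volume is net of what was instilled.

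The numbering of days also varies:

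- Section 2.3 equates day 1 with randomization, for example "To determine the change on inflammatory markers (WBC/CRP) from day 1 (randomization) to day 7", and does the same for the chest radiograph.
- The monitoring tables in Section 3.6 begin at Day 0. They place the baseline X-ray and CRP there, with no Day 1 entry for either.
- The drainage tables run Baseline, Day 1, Day 2, Day 3. The rows "Cumulative pleural fluid drained post pleural irrigation" and "Cumulative pleural fluid drained post IPFT" are ticked at Day 3 only and carry no hour label.

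The Data Collection Sheet, as shown, opens with "Date of admission" and has a discharge date, but no date or time of randomization.

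Two other outcomes have more than one starting point. Section 2.3 counts hospital stay from randomization, while the sheet counts it from the first t-PA/DNase dose or first irrigation. The treatment-failure definition in Section 3.6 counts 30 days for surgery from randomization, while the sheet again counts from first treatment.

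**The concern.** A single primary outcome with two time points is not pre-specified. Section 3.1 describes an open-label study and net volumes are recorded each day, so whoever runs the analysis could see both totals by arm before settling on one.

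The two windows also measure different things. Irrigation is described as follows: "Pleural irrigation will be performed minimum of 3 installations and maximum of 9 installation (3 times per day". The longest courses therefore need a third day. The number of t-PA/DNase doses is not fixed either: "The number of installation of intrapleural t-PA/DNase depends on the discretion of the treating physician". Crossover is allowed at any point, so a later cut-off admits more of it. With these features acting together, neither the direction nor the size of the difference between a 48-hour and a 72-hour result can be predicted from the documents.

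For hospital stay and surgery, a clock that starts at first treatment gives no start date for a patient who is randomized but never treated. That does not fit the intention-to-treat analysis named in Section 3.6.

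**Working it through.** **1. Does any other section fix the window?**

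| Place | What it gives |
|---|---|
| 2.2 Primary Objective | 48 h from randomization |
| 2.4 Hypothesis 1 | more drainage with IPFT; no time |
| 3.3 Sample size | failure rates 0.15 and 0.32; no drainage volume, no time |
| 3.6 Medication Regimen | 72 h from randomization |
| 3.6 drainage tables | cumulative total at Day 3, labelled by treatment |
| Statistical Analysis | no primary outcome, no time |

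Both hour figures are current text, and nothing in the text as available reconciles them.

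**2. What does Day 3 mean?**

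- Day 1 is randomization (Section 2.3) and Day 3 is a time point: (3 − 1) × 24 = 48 h.
- Day 0 is randomization (a possible reading of the monitoring tables): (3 − 0) × 24 = 72 h.
- Days 1 to 3 are three full 24-hour collection periods: 3 × 24 = 72 h.

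The field is compatible with either stated time. Its labels count from treatment, and Section 3.6 leaves the start of t-PA/DNase to the chest physician, so even the clock's origin is open.

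**3. Do the windows differ in substance?** At 3 irrigations per day, a course of n takes n/3 days, rounded up: 3 takes 1 day, 4 to 6 take 2 days, and 7 to 9 take 3 days. Of the 7 permitted course lengths, 3 extend into a third day. At 250 ml each, the saline to be subtracted is at most 2 × 3 × 250 = 1500 ml by 48 h and 3 × 3 × 250 = 2250 ml by 72 h. That is up to 750 ml more in the irrigation arm, if irrigation starts at randomization.

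**4. What could choosing the window do to the error rate?** The documents give no figures for this step, so it is illustrative. Let Z₁ and Z₂ be the test statistics at 48 h and 72 h under no treatment difference, bivariate normal with correlation ρ. The error is P(|Z₁| > 1.96 or |Z₂| > 1.96).

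| ρ (assumed) | Better window reported, undisclosed | Both tested openly at 0.025 |
|---|---|---|
| 0.95 | 6.5% | 3.3% |
| 0.90 | 7.0% | 3.6% |
| 0.80 | 7.8% | 4.0% |

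To see which ρ is plausible, assume daily net volumes with equal variance and between-day correlation r. In units of the daily variance, the 48 h total has variance 2 + 2r, the 72 h total has 3 + 6r, and their covariance is 2 + 4r. So

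ρ = (2 + 4r) / √[(2 + 2r)(3 + 6r)].

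- r = 0: 2/√6 = 0.816, error 7.7%
- r = 0.3: 3.2/√(2.6 × 4.8) = 0.906, error 7.0%
- r = 0.5: 4/√(3 × 6) = 0.943, error 6.6%

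The Bonferroni rule in the Statistical Analysis section would keep the error below 5% only if both windows were declared and tested.

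**The case against.** The strongest reply is that the plan leans towards 72 hours. The drainage tables have a baseline column and three daily columns, and the total is taken at Day 3. If each day is a full 24-hour collection, the total covers 72 hours whatever randomization is called. The maximum of 9 irrigations also fits three days, and the day 1 label in Section 2.3 is attached to the radiograph and inflammatory markers, not to drainage. This is fair as a guess at intent. But no passage states it, and the primary objective itself says 48 hours.

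The flow chart and other figures are not visible, and the data sheet may be incomplete as shown. Either could define Day 0 or carry a randomization time. That limits what can be said about the sheet. It does not remove the conflict between the two sections.

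The surgery conflict is weaker than the one on hospital stay. Randomization is named as the origin only in the treatment-failure definition, and the surgery outcome itself names none. The two documented origins still differ, but this is a secondary matter.

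The comparison in substance rests mainly on one arm. The timetable in Appendix 1 runs from one morning to the next, so t-PA/DNase given on it would end at about 24 hours, although Section 3.6 leaves the number of doses to the physician. The irrigation day count assumes full 24-hour days, and counting course lengths says nothing about how many patients receive each.

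The error rates depend on assumed correlations and on undisclosed selection. If the third day's variance were a quarter of the others, ρ would be 0.94 to 0.98 and the error 6.6% to 5.9% for r from 0 to 0.5. They show a mechanism and are not a forecast.

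**Conclusion.** The concern holds, and it must be fixed before analysis. The primary outcome has two stated times 24 hours apart, and neither the Day 3 field nor any other available text selects one. This conclusion comes from the text alone and needs no numerical assumption.

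The possible inflation, from 5% to roughly 6.5% to 7.8% for correlations of 0.95 to 0.8, supposes that the more favourable window is reported without disclosure. No direction of bias between the arms is claimed. The conflicting origins for hospital stay and 30-day surgery are real but of lower weight.

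**What to change.** Before any outcome data are examined by arm:

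1. Name one primary time point and state it identically in Section 2.2, Section 3.6, the Statistical Analysis section and the data sheet. 72 hours is a reasonable choice because it covers every permitted irrigation course that starts promptly; 48 hours can be kept as a named secondary outcome. The drawback of 72 hours is that more crossover can occur and dilute the contrast. Either time is workable if it is fixed in advance.
2. Define Day 0 and Day 1 relative to randomization and use that numbering throughout.
3. Add the date and time of randomization to the data sheet if they are not already recorded, and label the cumulative drainage field in hours from randomization for both arms.
4. Count hospital stay and 30-day surgery from randomization for every randomized patient. Do the same for 30-day mortality for consistency: the sheet starts it at first treatment, and Section 2.3 names no origin.

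The cost is protocol wording, relabelled fields and one added entry. Daily volumes are already collected, so no new measurement is needed.

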### 2.3 Secondary Objectives:

- To determine the reduction of pleural opacity (in percentage) on chest radiograph from day 1 (randomization) to day 7
- To determine the change on inflammatory markers (WBC/CRP) from day 1 (randomization) to day 7
- To determine the outcome :
  - Length of hospital stay (in days) after randomization for each group
  - The need of surgical intervention in 30 days
  - Adverse effects following t-PA/DNase and pleural irrigation
  - Mortality rate at 30 days

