## 2.4 Study Hypothesis

1. Subjects in the IPFT has more volume of pleural fluid drainage compared with pleural irrigation group
2. Subjects in the IPFT has greater reduction of inflammatory parameters compared with pleural irrigation group
3. Subjects in the IPFT has shorter length of hospital stay compared with pleural irrigation group
4. Subjects in the IPFT has less surgical referral rate compared pleural irrigation group
5. There is no difference of mortality rate between both groups

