### 3.7 Study protocol /flow chart

### 3.7 Statistical Analysis

Statistical analysis will be performed using the available SPSS software version 19. All numerical data will be subjected to normality testing using Shapiro-Wilk test. All normally distributed data will be expressed as mean  $\pm$  standard deviation (SD) whereas non-normally distributed data were expressed as median (IQR). For normally distributed data, parametric test with Student's t-test will be used. For non-normally distributed data, the Mann-Whitney test will be used or equivalent nonparametric tests. Within groups, the Wilcoxon rank sum test will be used. For qualitative data, Chi-Square test and Fisher's Exact test will be used. The significant p-value will be taken as  $<0.05$  or in the case of multiple comparisons it will be adjusted with a Bonferonni correction.

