## **OBSERVATION AFTER ADMINISTRATION OF t-PA (ALTEPLASE) & DNase (PULMOZYME)**

1. Observe the patient for:
  - a. deterioration in clinical condition
  - b. tension pneumothorax
  - c. hemorrhage from site or excessive drainage (in excess of 1L per hour) in drainage bottle
2. Monitor for:
  - a. Bedside ultrasound of thorax (by chest physician) daily with curvelinear probe (ultrasound Mindray, model Z5) by measuring the maximum distances between the parietal and visceral pleural.
  - b. Serial chest x-ray (baseline x-ray, day 7 post t-PA/DNase and pleural irrigation)
  - c. Serum CRP level (baseline, day 7 post t-PA/DNase and pleural irrigation)
  - d. FBC (baseline, day 1- 3, day 7 post t-PA/DNase and pleural irrigation). Drop of

hemoglobin by less than 10% from baseline is acceptable.

- e. Systemic bleeding/ Pleural bleeding
  - f. Drainage of pleural effusion daily
3. Stop the t-PA & DNase if there is significant drop of haemoglobin (>10% drop Hb) with clinical signs of shock or significant haemorrhagic fluids drained. Consider CTA and blood transfusion in those cases

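### WBC is scheduled at five time points but compared as an unadjusted two-point change, which forgoes baseline adjustment and drops patients without a Day 7 value

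*Combined protocol and SAP*

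**What the plan says.** Section 2.3 sets the outcome as "To determine the change on inflammatory markers (WBC/CRP) from day 1 (randomization) to day 7". Section 2.4 makes it a between-arm claim: "Subjects in the IPFT has greater reduction of inflammatory parameters compared with pleural irrigation group".

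The monitoring grids in section 3.6 tick the full blood count, including WBC, at Days 0, 1, 2, 3 and 7 in both arms. Appendix 1 agrees: "FBC (baseline, day 1- 3, day 7 post t-PA/DNase and pleural irrigation". CRP is sparser: "Serum CRP level (baseline, day 7 post t-PA/DNase and pleural irrigation".

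The between-arm tests in section 3.7 are "For normally distributed data, parametric test with Student's t-test will be used" and "For non-normally distributed data, the Mann-Whitney test will be used or equivalent nonparametric tests". The within-arm test is "Within groups, the Wilcoxon rank sum test will be used". The section names no repeated-measures model, no baseline covariate and no rule for a missing Day 7 value.

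**The concern.** Change to Day 7 is one number per patient and uses two of the five scheduled WBC values. This has two consequences.

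- **Precision.** An unadjusted change score subtracts the whole baseline value however weakly baseline predicts Day 7. When that correlation is well below 1, subtraction adds noise that a baseline covariate would not.
- **Missing Day 7 values.** A patient without a Day 7 count contributes nothing, even with up to four earlier counts on file. Section 2.4 expects earlier discharge in one arm: "Subjects in the IPFT has shorter length of hospital stay compared with pleural irrigation group". The only contact after discharge that section 3.6 describes is at Day 30. If patients go home before Day 7 because they are improving, and more of them do so on IPFT, the patients left in the comparison are a selected group, and the selection works against the second hypothesis.

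At stake is the WBC half of one secondary hypothesis, in a trial of 39 per arm where precision is scarce.

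**Working it through.** **Inputs.** From the documents: 39 per arm (section 3.3), the visit days, the two-point outcome and the tests. The plan gives no figure for the WBC comparison, so there is none to reproduce. The 39 is taken as printed; how it was derived is a separate matter. Assumed, because the documents give nothing: WBC SD 5 (x10^9/L); correlation rho of 0.6 to 0.9 between successive scheduled visits, decaying by visit, so that Day 0 and Day 7 correlate at r = rho^4; a true Day 7 difference of -2.

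**Step 1. Complete data, closed form.**

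- SE of the change score = SD x sqrt(2/39) x sqrt(2(1 - r))
- SE adjusted for baseline = SD x sqrt(2/39) x sqrt(1 - r^2)
- Ratio = sqrt((1 + r)/2)

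With SD x sqrt(2/39) = 5 x 0.2265 = 1.132:

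| rho | r = rho^4 | SE, change | SE, adjusted | Reduction |
|---|---|---|---|---|
| 0.6 | 0.130 | 1.49 | 1.12 | 25% |
| 0.7 | 0.240 | 1.40 | 1.10 | 21% |
| 0.8 | 0.410 | 1.23 | 1.03 | 16% |
| 0.9 | 0.656 | 0.94 | 0.85 | 9% |

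Simulation gives about 9-24%. With nothing missing, an all-days model gives the same SE as baseline adjustment (1.10 for both at rho 0.7), so none of this gain comes from Days 1-3.

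**Step 2. Some Day 7 loss.** 3000 simulated trials per setting, about 22% v 28% missing, with the chance of loss depending on Day 3 WBC:

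| rho | SE, change | SE, baseline-adjusted | SE, all days | Adjusted v change | All days v adjusted |
|---|---|---|---|---|---|
| 0.6 | 1.76 | 1.28 | 1.29 | 27% smaller | 1% larger |
| 0.7 | 1.59 | 1.25 | 1.22 | 21% smaller | 2% smaller |
| 0.8 | 1.39 | 1.12 | 1.10 | 19% smaller | 2% smaller |
| 0.9 | 1.09 | 0.96 | 0.90 | 12% smaller | 6% smaller |

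A repeat at rho 0.7 gave 1.61, 1.27 and 1.25. Across repeats, baseline adjustment cut the SE by about 11-28%, and Days 1-3 changed it by a further -1% to 8%.

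**Step 3. Bias under the same kind of loss.** The change score among observed patients falls short by about 4-9%, or 0.08 to 0.18 on a difference of 2. Baseline adjustment alone does not cure this. In one run with 21% v 27% missing, the baseline-adjusted estimate in observed patients was -1.77 to -1.85, that is 0.15/2 = 7.5% to 0.23/2 = 11.5% too small, while the all-days estimate was -1.97 to -2.03. Days 1-3 are needed for the bias and baseline for the precision.

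**Step 4. Loss that differs strongly by arm.** With 10/30%, 20/40% or 30/50% missing (control/IPFT), the two-point comparison keeps between 39 x 0.9 + 39 x 0.7 = 62 and 39 x 0.7 + 39 x 0.5 = 47 of 78 patients. Its estimate becomes -1.5 to -1.8 for a true -2.0, and +0.2 to +0.5 for a true 0. The all-days estimate stays at -1.98 to -2.02, or about 0. With equal 10% loss there is almost no bias.

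**The case against.** The strongest reply is that a Day 7 change is a legitimate, readable outcome that matches the Day 7 elements of the treatment-success definition in section 3.6, and that everything said about loss is conjecture. Both arms have a full blood count scheduled on Day 7. Nothing says discharged patients are not sampled, and no distribution of discharge times is given. The simulated recovery to -2 is also partly built in: loss was made to depend on the observed Day 3 WBC, which is the condition under which the all-days model is unbiased. All of that stands. It limits the bias argument to a conditional one, and against an SE of about 1.6 a bias of 0.2 or less is small. It does not touch the precision argument, which holds with complete data.

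Two stronger readings are tempting. A reader might infer that the 9-28% gain in precision is lost because Days 1-3 are discarded. Steps 1 and 2 show that nearly all of it comes from baseline adjustment. A reader might also infer that patients whose WBC has already fallen will be missing at Day 7. The documents do not say so. It is an inference from the expected shorter stay and the absence of any described contact between discharge and Day 30.

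Nor are the Day 1-3 counts wasted: the same blood test serves haemoglobin safety monitoring. They are only unused for this comparison.

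**Conclusion.** The point holds as a modest improvement to a secondary analysis. The planned unadjusted two-point change is less precise than the collected data allow: the SE could be about 9-24% smaller with complete data and 11-28% smaller with some Day 7 loss, nearly all of it from using baseline as a covariate. The counts on Days 1-3 add little precision. Their value is protection against a bias of about 4-9%, larger if loss differs strongly by arm, and only if Day 7 values are missing in relation to earlier WBC.

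Every size here rests on assumed SD, correlations and loss. The direction of the precision result needs only a Day 0 to Day 7 correlation below 1. The documents do not support saying that such loss will occur or how large it would be, nor that the test of the second hypothesis is invalid as planned.

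**What to change.** 1. **Settle the baseline day.** Section 2.3 treats Day 1 as randomization, while the grids put baseline at Day 0 and do not measure CRP on Day 1. Reconcile these and define baseline as the pre-treatment value. Otherwise a baseline count could be modelled as an outcome.
2. **WBC, in section 3.7.** Use a mixed model for repeated measures (SPSS MIXED) with the post-baseline values through Day 7 as outcomes; arm, day, arm-by-day and baseline WBC as fixed effects; unstructured covariance; log scale if skewed. Let the baseline slope vary by day, since its correlation with later values falls over time and the all-days figures above allow for this. Report the Day 7 arm difference with 95% CI.
3. **Deaths and missing values.** Report deaths before Day 7 by arm next to the result, because the model implicitly projects a WBC for those patients. Give the number with a Day 7 value in each arm.
4. **CRP.** Compare at Day 7 adjusted for baseline. There are no intermediate values to offset a missing Day 7 CRP.

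The cost is a few lines of text and a little more analysis in the software already named, with no extra measurements. The drawback is the assumption that missing Day 7 values are explained by the observed ones; the planned analysis of observed patients needs a stronger one.
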